### **10.2. Plasma, Leukocyte, Dried Blood Spot GCase Activity**

Sample collections that have an actual sampling time that deviates from the predefined collection time windows will be flagged in the data listings.

The following visit windows will be applied for the GCase sample collections:

Screening: +/-1 week

Weeks 1 to 12: +/-1 day

Weeks 14, 16, 20, 24, 28, 32, 38: +/-3 days

Week 38: +/-1 weeks

Individual GCase activity levels will be presented in data listings. A summary statistic for observed and changes from baseline values will be presented by study part, matrix, cohort, and overall.

Individual GCase raw activity levels will be plotted by-participant over time.

### **10.3. Plasma, Leukocyte and DBS Pharmacokinetic Parameters**

Plasma, leukocyte, and DBS GCase baseline adjusted activity level-time data will be analyzed by non-compartmental analysis using Phoenix® WinNonlin® Version 8.3 or higher (Certara USA, Inc., Princeton, NJ). The following PK parameters will be calculated for baseline adjusted GCase activity levels, where data permit:

$C_{\max}$	Maximum observed concentration.
$T_{\max}$	Time of maximum observed concentration.
$AUC_{\text{last}}$	AUC from time 0 to the last measurable observed concentration ( $C_{\text{last}}$ ), calculated using the linear trapezoidal rule.

Actual sampling times will be used for the estimation of all PK parameters, and all available GCaSe activity level data will be included in the analysis (including resulting from samples collected outside predefined collection windows).

Plasma, leukocyte, and DBS PK parameters will be presented in data listings and summarized separately using descriptive statistics (number of observations, arithmetic mean, SD, CV, geometric mean, geometric CV, median, minimum, and maximum) by study part and cohort.  $T_{\max}$  will be summarized using number of observations, median, minimum, and maximum only.

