Investigational Product and Mode of Administration: FLT201 Solution for Infusion will be given as a single dose, slow IV infusion over up to 2 hours.	
Non-investigational Medicinal Product: The non-investigational medicinal products are prednisolone (prednisone), methylprednisolone, and tacrolimus.	
Maximum Duration of Participant Involvement in the Study: The planned total study duration for each participant is up to 56 weeks comprising: 
 • Screening period of up to 16 weeks • Dosing day for FLT201 infusion • Post-dose follow-up period of 38 weeks (+2-week window) All participants will be subsequently followed up for at least a total of 5 years post-dosing under a separate long-term follow-up protocol.	
Statistical Methods: Sample size is based on feasibility and not formal hypothesis testing. All statistical analysis will be descriptive. The dose escalation scheme as described is intended to minimize the number of participants that may be dosed at suboptimal levels, whilst allowing for safety evaluation and option to expand each cohort where DLT is observed.	
Protocol Version and Date: v8.0 (16 November 2023)	

Table 1: Schedule of Assessments (Screening and Weeks 1 to 38/EOS)

Procedure	Screen 1 ^A	Screen 2 ^A		Week																		Unscheduled Visit ^S	
				1	2	3	4	5	6	7	8	9	10	11	12	14	16	20	24	28	32		38/ EOS ^R
Visit Window	-16 to -2 wk	-3 wk ± 1 wk		± 1 day												± 3 days						±2 wk	
Informed consent	X		For Day -1 to Day 3 see Table 2																				
Demography & medical history	X																						
Prior & concomitant medications	X	X		X	X	X	X	X	X	X	X	X	X	X	X	X	X	X	X	X	X	X	
Adverse events	X	X		X	X	X	X	X	X	X	X	X	X	X	X	X	X	X	X	X	X	X	
Gaucher disease & ERT/SRT history	X																						
Gaucher disease severity (GD-DS3)		X												X				X			X		
Physical examination ^C	X			X	X	X	X	X	X	X	X	X	X	X	X	X	X	X	X	X	X	X	
Vital signs ^D	X			X	X	X	X	X	X	X	X	X	X	X	X	X	X	X	X	X	X	X	
12-lead ECG	X				X									X				X			X		
MRI: liver & spleen size		X												X				X			X		
MRI: bone marrow burden		X												X				X			X		
DEXA (Z-score, T-score; lumbar spine, hip)		X																			X		
BPI-SF, diary completion ^E	X	X				X								X				X			X		
FACIT-Fatigue completion ^F	X	X				X								X				X			X		
HRQoL (SF-36)		X																			X		
Chest x-ray & pulmonary function tests		X												X				X			X		
Immunosuppressants ^G																							
Local Laboratory Tests																							

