15.4 Analysis of Secondary Endpoints

Efficacy

The following secondary efficacy endpoints will be summarised by cohort/dose level.

- Change from baseline to each assessment point in lyso-Gb1 in plasma.
- Change from baseline to each assessment point in spleen volume by MRI.
- Change from baseline to each assessment point in liver volume by MRI.
- Change from baseline to each assessment point in haemoglobin.
- Change from baseline to each assessment point in platelet count.

Pharmacokinetic

Change from baseline in plasma and leukocyte GCase activity will be summarised by cohort/dose level and plotted by participant and overall. The area under curve (AUC) of GCase activity will be calculated from baseline to Week 38 and summarised. The details of derivations of the AUC using a linear trapezoidal rule will be provided in the SAP.

Shedding

Clearance of vg in plasma, saliva, urine, stool, and semen will be summarised by cohort/dose level.

Immune Response to Transgene Product

Immune response to the GCase transgene product measured as change from baseline in total anti-GCase antibody titre and neutralising antibody titre will be summarised by cohort/dose level and plotted.

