## 1. Introduction

FLT201 is an investigational AAV-gene therapy administered as a single dose, slow intravenous (IV) infusion, that is being developed as a treatment to improve the clinical phenotype in patients with Gaucher disease type 1.

The aim of this first-in-human, Phase 1/2, open-label study is to evaluate the safety, tolerability, efficacy, and pharmacokinetics of FLT201, and to investigate the relationship of FLT201 dose to augmentation of residual glucocerebrosidase (GCase) expression (activity and concentration), and its potential to improve the clinical phenotype by reduction of cellular accumulation of GCase substrate.

The purpose of this statistical analysis plan (SAP) is to define the planned statistical methods consistent with the study objectives. This plan should be read in conjunction with the study protocols (Global (ex-US/ex-Brazil), US only and Brazil only) and is prepared in compliance with International Conference on Harmonisation (ICH). All analyses will be conducted using SAS® Version 9.4 or higher (SAS Institute Inc., Cary, North Carolina).

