**Table 2-1 Primary Objective and Endpoints - Safety**

Primary Objective	Primary Endpoints
To assess the safety and tolerability of a single IV administration of FLT201 in adults with Gaucher disease type 1 (previously treated and previously untreated).	
Primary safety variable: incidence of TEAEs (including DLTs) from Day 1 to the last follow-up visit.
 
Other safety endpoints: incidence of AEs, SAEs, and changes from baseline in vital signs, 12-lead ECG, physical examination, and laboratory assessments from Day 1 to the last follow-up visit.

Abbreviations: AE=adverse event; DLT=dose-limiting toxicity; ECG=electrocardiogram; IV=intravenous; SAE=serious adverse event; TEAE=treatment emergent adverse event.
	

Table 2-2 presents the secondary objectives and endpoints.

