**Table 2-3 Exploratory Objectives and Endpoints**

Exploratory Objectives	Exploratory Endpoints
Other efficacy/biomarkers: To assess the impact of FLT201 on: 
 
Gaucher disease severity and progression
 
bone disease
 
fatigue
 
pain
 
biomarkers
 
lung disease
 
	Change from baseline to each assessment point in: 
 
Gaucher disease severity measured by the Gaucher disease severity score (GD-DS3)
 
bone marrow burden score measured by MRI
 
bone mineral density measured by dual energy x-ray absorptiometry (DEXA) 
 
Z-score & T-score at lumbar spine; hip (left and right)
 
 
 
fatigue measured by FACIT-Fatigue
 
pain measured by Brief Pain Inventory- Short Form (BPI-SF)
 
disease activity biomarkers: chitotriosidase, CCL18
 
bone biomarkers: bsALP, osteocalcin
 
chest x-ray and pulmonary function tests
 

Pharmacokinetic: To characterize the pharmacokinetics of FLT201.	
 
AUC, peak, and steady state GCase activity levels in plasma and leukocytes (baseline to Week 38)
 
Change from baseline to each assessment point in GCase concentration (antigen levels)
 
Dose response relationship
 

Immunologic: To describe the immune response to AAVS3 capsid proteins.	
 
Immune response to AAVS3 capsid (AAVS3 antibody titer and T-cell response)
 
Change from baseline to each assessment point in immune response biomarkers
 

HRQoL: To assess the impact of FLT201 on health-related quality of life (HRQoL).	Change from baseline to each assessment point in HRQoL measured by SF-36.
Abbreviations: AAVS3=adeno-associated viral vector serotype S3; AUC=area under curve; BPI-SF=Brief Pain Inventory – Short Form; bsALP=bone-specific alkaline phosphatase; DEXA=dual energy x-ray absorptiometry; FACIT-Fatigue=Functional Assessment of Chronic Illness Therapy - Fatigue scale; GCase=glucocerebrosidase; HRQoL=health-related quality of life; MRI=magnetic resonance imaging.	

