#### **7.2.2. Concomitant Medications**

Concomitant treatment refers to all treatment taken between the date of IMP infusion and the end of study visit (Week 38 for all participants excluding US and Month 24 for participants in the US only) inclusive.

Concomitant medication includes prescription and non-prescription medication and herbal treatments. Concomitant medication also includes immunosuppressants used as part of an immune management and monitoring regimen. If immunosuppressant drugs are used, tacrolimus levels will be monitored, and data will be presented (see [Section 9.6.2](#)).

Concomitant medications will be summarized using ATC Level 4 (if this is not available, the closest ATC level will be used) by preferred term, study part, dose cohort, and overall. Rules on imputation of incomplete dates are found in [Section 4.1](#).

In addition, participants immunosuppressant drug dose levels will be plotted over time for all participants who received at least one dose of any immunosuppressant drugs described in the protocol.

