### **9.1.1. Treatment Emergent Adverse Events**

A TEAE is defined as an AE that meets any of the following conditions:

- begins during or after the infusion
- begins before the infusion and worsens in severity during or after the infusion
- is completely missing an onset date and end date
- is completely missing an onset date and the end date is on or after the date of infusion

All adverse events will be classified by SOC and preferred term according to MedDRA (Version 26.1 or higher).

An overview summary of the number and percentage of participants with any AE, any TEAE, serious TEAE, non-serious TEAE, IMP-related TEAE, IMP-related serious TEAE, TEAE leading to treatment discontinuation, and AE leading to death will be provided by study part, dose cohort, and overall. This summary will also be used for Lay Person summary part of the EU CTR reporting. A listing for all AEs will also be presented.

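### SAP 10.3 runs AUC to each participant's last sample instead of Week 38, and crude TEAE percentages pool Week 38 with Month 24 follow-up

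*SAP*

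**What the plan says.** One SAP covers three protocols: global, US only and Brazil only (SAP section 1). SAP 7.2.2 places the end-of-study visit at "Week 38 for all participants excluding US and Month 24 for participants in the US only". US participants can enter Part 1 only (SAP 3.1).

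**AUC.** Protocol 15.4 says that the AUC of GCase activity "will be calculated from baseline to Week 38 and summarised". SAP Table 2-3 repeats that period for its exploratory endpoint: "AUC, peak, and steady state GCase activity levels in plasma and leukocytes (baseline to Week 38". The derivation in SAP 10.3 is different: "AUC from time 0 to the last measurable observed concentration". It takes in all available data, including samples outside the collection windows. SAP 10.4 regresses the log of AUClast, and of Cmax, on log dose in Part 1. Dose is the only covariate.

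**Adverse events.** The primary safety variable is "incidence of TEAEs (including DLTs) from Day 1 to the last follow-up visit" (SAP Table 2-1). SAP 9.1 collects events up to the end-of-study visit. SAP 9.1.1 sets no upper time limit for a TEAE and plans "An overview summary of the number and percentage of participants with any AE, any TEAE, serious TEAE" and further categories, by study part, dose cohort and overall. The SAP plans no exposure-adjusted rate, common cut-off or regional split for these tables.

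**The concern.** An AUC grows with the time over which it is taken. Once the Week 38 limit is dropped from the derivation, two participants with the same activity profile have different AUClast values if one is sampled for longer. Sampling length can differ for three reasons: early withdrawal; the monthly unscheduled visits that Protocol 12.4 requires while entry to the long-term study is delayed; and possibly country, through the Month 24 visit in the US. In a power model on about 12 participants, a difference in sampling length between cohorts is read as a departure from dose proportionality.

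Crude incidence behaves in a similar way. A cohort with more US participants has more time in which events can be counted, so at equal toxicity it is expected to show a higher percentage. The primary safety summary compares cohorts on these percentages. The events most exposed are late or less common ones, such as SAEs and some AESIs, which carry much of the interest after a one-time gene therapy.

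**Working it through.** The plan gives no figure to reproduce here, because the sample size rests on feasibility. The check compares the texts and then sizes the effect under stated assumptions.

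**1. The texts on AUC.** Protocol 15.4 and SAP Table 2-3 say baseline to Week 38. SAP 10.3 says last measurable value, all data. Protocol section 15 requires departures from its planned analyses to be detailed in the SAP. SAP section 14 lists four changes, and this is not one of them.

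**2. Follow-up ratio.** Week 38 is 38 × 7 = 266 days. Month 24 is 24 × 30.4375 = 730.5 days, or 104.36 weeks. The ratio is 730.5/266 = 2.75.

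**3. AUC ratio, if US GCase sampling runs to Month 24 (assumption).** Assume that activity rises linearly to a plateau of 1 at Week 4.
- Stable plateau: AUC(T) = 2 + (T − 4) = T − 2 weeks. The ratio is (104.36 − 2)/(38 − 2) = 102.36/36 = 2.84.
- Decline with half-life h weeks: AUC(T) = 2 + (h/ln 2)[1 − 2^(−(T−4)/h)].

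| Half-life (weeks) | AUC to Month 24 / AUC to Week 38 |
|---|---|
| none (stable) | 2.84 |
| 104 | 2.32 |
| 52 | 1.95 |
| 26 | 1.52 |
| 13 | 1.17 |

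Early withdrawal needs no US assumption. If sampling stops at Week 20 on a stable plateau, AUClast is (20 − 2)/(38 − 2) = 0.50 of the Week 38 value.

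**4. Effect on the power-model slope.** The inputs are the four planned doses (4.5×10^11, 1.3×10^12, 3.9×10^12 and 1.1×10^13 vg/kg), 3 participants per cohort (assumption) and true β = 1. With x = ln(dose) measured from the lowest dose, x = 0, 1.061, 2.160, 3.196. The mean is 1.604 and Σ(x − mean)² = 5.712. If cohort k is entirely US and the others are not, the slope moves by ln(ratio) × (x_k − mean)/5.712. At ratio 2.84, ln = 1.045.
- Only Cohort 4 US: 1 + 1.045 × 1.592/5.712 = 1.29.
- Only Cohort 1 US: 1 − 1.045 × 1.604/5.712 = 0.71.
- One of the three Cohort 4 participants US: 1 + 0.291/3 = 1.10.
- One US participant in every cohort: 1.00.

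With a 52-week half-life (ratio 1.95, ln = 0.670), the first two become 1 + 0.670 × 0.279 = 1.19 and 1 − 0.670 × 0.281 = 0.81.

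**5. Crude event percentages, constant hazard (assumption).** p(Month 24) = 1 − [1 − p(Week 38)]^2.746.

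| By Week 38 | By Month 24 |
|---|---|
| 10% | 25% |
| 20% | 46% |
| 30% | 62% |
| 50% | 85% |
| 90% | 99.8% |

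For an event at 30% by Week 38, a cohort that is half US has an expected crude percentage of (30 + 62.5)/2 ≈ 46%.

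**6. With a Week 38 limit.** For participants followed to Week 38, the regional follow-up and AUC ratios are 1, the slope returns to 1.00, and the expected event percentage is the same in both regions.

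**The case against.** The strongest reply is on AUC. A reader might infer that AUClast is shown to depend on country and that the plan has no common AUC cut-off. The documents support neither. Week 38 is the stated end in two places; the fault is that SAP 10.3 does not carry it through. Nothing supplied shows GCase sampling in the US after Week 38. The windows in SAP 10.2 end there, and Month 24 appears only as an end-of-study visit in the concomitant-medication definition. Later US sampling is plausible but unproven.

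A reader might also take AUClast to be the only dose-response analysis. It is not. SAP 10.4 also models Cmax, and change from baseline in activity is summarised by cohort. Summaries by eCRF visit name are not affected by follow-up length. PK parameters are summarised by part and cohort, not overall, and the AUC and dose-response endpoints are exploratory. No document links cohort to country, so slopes of 0.7 and 1.3 are extreme allocations.

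On adverse events, the protocol's main expected risks come early: infusion reactions within hours, acute DLTs assessed in the first 4 weeks, and immunosuppression starting at about Week 3. Constant hazard would overstate the effect for such events, and the any-TEAE line may be near its ceiling by Week 38. Escalation uses a minimum of 4 weeks of data per participant, so these tables do not drive dosing, and every AE is listed. The SAP also follows the protocol's primary window faithfully.

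All of this stands, and it limits the size and severity of the point. It does not remove the unlisted change in the AUC derivation, or the mixing of two follow-up lengths in the cohort percentages for late or less common events.

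**Conclusion.** The point holds in two parts, as something that should be fixed in a descriptive, feasibility-sized study.

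- **AUC:** SAP 10.3 contradicts Protocol 15.4 and SAP Table 2-3, and the change is undeclared. This rests on the text alone. AUClast then depends on length of sampling, through withdrawal or visits after Week 38. Dependence on country is conditional on US sampling to Month 24. Under that assumption the AUC ratio is 1.2 to 2.8, depending on durability of expression. The fitted slope at true β = 1 lies between about 0.7 and 1.3 when only the lowest or only the highest of four cohorts is US, and is 1.00 under an even spread.
- **Adverse events:** crude TEAE, SAE and AESI percentages pool follow-up that differs 2.75-fold by region. The distortion is large for late or less common events if the hazard is roughly constant (10% to 25%, 30% to 62%). It is small for early events, and for any TEAE if nearly everyone has one early.

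It would go too far to conclude that the primary safety endpoint is invalid. Its window is stated and followed; what is missing is a like-for-like basis for comparing cohorts.

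**What to change.** (a) In SAP 10.3, define AUC and Cmax over time 0 to Week 38 and use these in SAP 10.4. Cmax belongs here because longer sampling gives more chances for a higher maximum. Where sampling stops earlier, report AUC divided by the sampled time and flag it. That value is on a different scale, so it should not be mixed with AUC to Week 38 in one regression.

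(b) Keep the stated primary window, Day 1 to the last follow-up visit. Add TEAE, SAE and AESI tables restricted to Day 1 to Week 38 for all participants, and name these as the basis for comparing cohorts. Present full follow-up as rates per person-year, with US events after Week 38 shown separately. The separate display matters because long follow-up dilutes a person-year rate when events cluster early.

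The cost is SAP wording and one extra set of tables. No new data are needed, since event dates, sampling times and country of enrolment are already part of the planned data and summaries. Adding tables beside the primary window leaves the primary endpoint unchanged.

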6.5.3.3 Potential Benefits

FLT201 has the potential to provide clinically relevant advantages for Gaucher disease participants:

- A single treatment with FLT201 is expected to lead to long-term production of GCase enzyme, avoiding the need of chronic administration of medication.
- The continuous production of functional GCase enzyme will avoid the brief peaks and prolonged troughs in plasma GCase levels that are seen with ERT/SRT and is expected to lead to improved clearance of lyso-GB1 and thereby an improvement in efficacy.
- Based on the fact, that GCase will be generated in the participant's own hepatocytes, the enzyme will have the participant's individualised glycosylation pattern. As such the potential for antibody development including the potential for the development of neutralising antibodies is reduced compared to ERT [[Mingozzi 2003](#)].
- Liver expression as a result of AAV gene transfer induces immune tolerance to secreted liver expressed human proteins. Tolerance induction is favoured by higher levels of transgene expression [[Mingozzi 2003](#)].

Currently available treatment options include ERT (Cerezyme[®] (imiglucerase) VPRIV[®] (velaglucerase) and Elelyso[®] (taliglucerase)) or SRT (Cerdelga[®] (eliglustat) and Zavesca[®] (miglustat)). Despite these treatments, there remains an unmet need due to incomplete efficacy and burden of therapy. All products require chronic, and potentially life-long administration.

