8.1 Study Description

This is a first in human, Phase 1/2, open label, safety, tolerability, and efficacy study in adult patients with Gaucher disease type 1.

Participants will undergo the screening assessments described in Section 12.1.1 and Section 12.1.2. for up to 16 weeks prior to Study Day 1 (gene therapy infusion).

In Part 1, eligible participants currently receiving ERT/SRT will maintain their current treatment until a minimum of 2 consecutive results at least 4 weeks post-dosing show leukocyte GCase activity level higher than pre-dose trough GCase activity level, after which ERT/SRT may be withdrawn.

Progression from Part 1 to Part 2 will be by a substantial protocol amendment, based on safety/tolerability (including DLT), PK, PD, and clinical data.

In Part 2, eligible participants will be PUPs. Participants may need to be considered for initiation of ERT/SRT in case of a lack of a trend to normalisation in leukocyte GCase activity level in serial measurements from at least 4 weeks post-dosing, suggestive of low probability of clinical efficacy.

Treatment-eligible participants will report to the infusion study site on the day prior to receiving the gene therapy infusion (Day -1). Participants will either attend their local study site if it has been approved for FLT201 infusion, or if not, an alternative approved infusion study site. On Day 1, FLT201 will be administered as a single-dose, slow IV infusion into a peripheral vein, and the participant will remain in the study centre for at least 8 hours until the investigator has deemed the participant as fit to be discharged.

Participants will be required to undergo study evaluations at intervals over the 9-month post -treatment period. These will take place either at the study infusion site or at their local study site.

The study will be conducted in 2 parts (Figure 3):

[figure not shown]

Figure 3: Study Schema

Part 1: Dose Escalation in Previously Treated Patients

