11.3.1 Discontinuation/Resumption/Commencement of ERT/SRT

ERT/SRT will be discontinued once GCase activity is in the normal range.

If, after the discontinuation of ERT/SRT, haemoglobin or platelet levels start to decline or if disease-specific biomarkers or other clinical signs and symptoms significantly worsen compared to baseline, then ERT/SRT will be resumed. This information will then inform future decisions for subjects as to the level of GCase activity at which ERT/SRT is to be withdrawn.

In addition, GCase expression loss as evidenced by decline in serial GCase activity measurements to baseline (pre-FLT201 dosing) levels, ERT/SRT will be resumed.

The decision to withdraw or restart ERT/SRT should be discussed with the Medical Monitor and Sponsor.

12 Study Procedures

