#### 10.4. Pharmacokinetic Statistical Analyses – Dose Proportionality (Power Model)

A non-linear Power Model will be used to assess dose-proportionality for baseline adjusted GCaSe Activity Levels in Part 1 of the study in all matrices (plasma, leukocytes, DBS). Actual dose received by each patient will be used. The proportional relationship between the expected value of each parameter  $E(y)$  and dose is written as a power function:

$$E(y) = \alpha * \text{dose}^{\beta} \text{ [Equation 1]}$$

where ' $\alpha$ ' is a constant, ' $\beta$ ' is the proportionality constant and ' $y$ ' is the parameter of interest. The exponent,  $\beta$ , will be estimated by performing a linear regression of  $\ln(\text{parameter})$  [ $C_{\max}$  and  $AUC_{\text{last}}$ ] versus  $\ln(\text{dose})$ . The exponent,  $\beta$ , is the estimated slope of the resulting regression line, since taking logs of Equation 1 gives the linear relationship:

$$\ln(y) = \alpha + \beta * \ln(\text{dose}) \text{ [Equation 2]}$$

The relationship is dose proportional when  $\beta = 1$ .

Linear regression plots of systemic exposure ( $C_{\max}$  and  $AUC_{\text{last}}$ ) versus dose will be presented using log-log scales with the power model overlaid.

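### The GCase exposure parameters and dose-proportionality slope have no rule for samples or baselines taken on ERT, so the slope is confounded in a direction the documents do not determine

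*SAP*

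**What the plan says.** **Parameters.** SAP 10.3 calculates Cmax, Tmax and AUClast on baseline-adjusted GCase activity in plasma, leukocytes and dried blood spots. Its inclusion rule is "all available GCaSe activity level data will be included in the analysis", and samples outside the collection windows are kept too.

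**Baseline.** SAP 10.1 subtracts, for each matrix, the mean of the screening and pre-dose results and sets negative values to 0.

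**Slope.** SAP 10.4: "A non-linear Power Model will be used to assess dose-proportionality for baseline adjusted GCaSe Activity Levels in Part 1 of the study". It regresses ln(Cmax) and ln(AUClast) on ln(dose) and reads proportionality as a slope of 1. It gives no interval or acceptance range.

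**ERT after dosing.** Part 1 enrols only patients on ERT or SRT (Protocol 9.1). Under Protocol 8.1, "eligible participants currently receiving ERT/SRT will maintain their current treatment until a minimum of 2 consecutive results at least 4 weeks post-dosing" exceed the pre-dose trough in leukocytes. Protocol 11.3.1 says "ERT/SRT will be discontinued once GCase activity is in the normal range", with no minimum time, and provides for resumption. Protocol 6.5.3.3 refers to "brief peaks and prolonged troughs in plasma GCase levels that are seen with ERT/SRT".

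**Safeguards.** The PK Set review (SAP 4.4.3) can remove whole participants case by case, with dosing errors as its example. Nothing in either document flags, excludes or models samples taken on ERT, or times post-dose samples to ERT infusions.

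**The concern.** ERT is recombinant GCase, the quantity that the assay measures. A Part 1 ERT user sampled after FLT201 but before withdrawal carries both transgene product and infused enzyme, and the derivation does not separate them. Cmax is the most exposed parameter because one sample near an infusion peak can set it. One averaged baseline per participant can offset a trough level but not a peak.

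The same baseline causes a second problem. It was measured on ERT, and it is still subtracted after ERT has been withdrawn, when the ERT part is no longer in the sample.

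The ERT amount does not scale with FLT201 dose, so either error weighs most where transgene expression is lowest. Time on ERT can also differ by cohort, since withdrawal depends on the GCase response.

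At stake is the only dose-exposure model in the SAP. It bears on the secondary objective of relating dose to endogenous GCase production and on the exploratory dose-response endpoint.

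**Working it through.** **1. The plan's own exposure figure.** Protocol 6.5.2 projects 76 to 295 nmol/h/mL plasma GCase at 4.5×10^11 vg/kg from 336 to 1308 at 2×10^12 vg/kg in macaques. Linear scaling gives 336 × 0.225 = 75.6 and 1308 × 0.225 = 294.3. The figure reproduces to within rounding.

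**2. Samples affected under Protocol 8.1.** With weekly visits the earliest qualifying pair is Weeks 4 and 5. The 38-week schedule has Day 3, Weeks 1 to 12 and seven later visits: 1 + 12 + 7 = 20 post-dose samples. Day 3 plus Weeks 1 to 5 is 6, so 6/20 = 30% for an ERT user. Protocol 11.3.1 supports no such minimum.

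**3. Set-up for the slope.** Planned doses are 4.5×10^11, 1.3×10^12, 3.9×10^12 and 1.1×10^13 vg/kg (Protocol 13.3.1), in ratios r = 1, 2.889, 8.667 and 24.444. Cohorts are of equal size and there is no noise. FLT201 activity is taken as exactly proportional to dose and flat over time, so the true slope is 1. ERT sizes are assumptions in multiples of Cohort 1 FLT201 activity:

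- c: ERT activity above baseline in on-ERT post-dose samples
- b: ERT activity contained in the baseline

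The slope is least squares of ln(y) on ln(r). The values of ln(r) are 0, 1.061, 2.159 and 3.196, with mean 1.604 and Sxx = 5.712.

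**4. Post-dose increment only (b = 0).** For Cmax, y = r + c. At c = 1, ln(y) = 0.693, 1.358, 2.269 and 3.236, so Sxy = 4.563 and the slope is 4.563/5.712 = 0.80. For AUClast with ERT present for 5 of 38 weeks, y = 38r + 5c.

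| c | Cmax slope | AUClast slope |
|---|---|---|
| 0.1 | 0.97 | 0.996 |
| 0.5 | 0.88 | 0.98 |
| 1 | 0.80 | 0.96 |
| 3 | 0.60 | 0.90 |

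At the projected Cohort 1 level, c = 1 is 76 to 295 nmol/h/mL and c = 3 is 228 to 885.

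**5. On-ERT baseline only (c = 0).** For AUClast with 33 weeks off ERT, y = 38r − 33b. For a Cmax taken after withdrawal, y = r − b.

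| b | AUClast slope | Cmax slope, off-ERT samples |
|---|---|---|
| 0.1 | 1.03 | 1.03 |
| 0.25 | 1.07 | 1.08 |
| 0.5 | 1.17 | 1.20 |

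**6. Both together, AUClast.** y = 38r + 5c − 33b. With c = 1 and b = 0.25 the slope is 1.03. With c = 5 and b = 0.25 it is 0.89. The sign of the error depends on two unknowns.

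**7. ERT/SRT mix.** SRT users receive no infused enzyme. If c = 1 applies only in the two lower cohorts, the Cmax slope is 0.78. If it applies only in the two upper cohorts, it is 1.02.

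**The case against.** A reader might infer that the plan necessarily flattens the slope and that a proportional response will be reported as clearly less than proportional. The documents do not support that. The on-ERT baseline removes trough ERT from on-ERT samples and over-subtracts later, which pushes the slope up. Nothing cited says how samples fall relative to infusions. ERT is given every two weeks and its peaks are described as brief, so many samples may sit near trough. Collection details are left to a laboratory manual that is not among the documents. With no acceptance range in SAP 10.4, a phrase such as clearly less than proportional has no defined meaning. These points stand.

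It also stands that AUClast moves little if ERT ends near Week 5, and that five weeks on ERT is a minimum under Protocol 8.1 only. The 38-week figures do not carry over to US participants, whom SAP 7.2.2 follows to Month 24.

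The consequence is bounded. All analysis is descriptive, dose response is exploratory, and the Part 2 dose is chosen from all Part 1 data with DMC input, not from this slope. Raw by-participant GCase plots and ERT/SRT listings would let a careful reader see some of the effect.

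None of this supplies the missing rule. Plots and listings do not correct Cmax, AUClast or the slope, and the PK Set review works on participants, not samples. An unknown direction also makes the single planned slope harder to interpret.

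**Conclusion.** The point holds as a gap in the analysis rules. All GCase samples enter Cmax, AUClast and the Part 1 slope, with no handling of on-ERT samples or of an on-ERT baseline. ERT activity above baseline is counted as FLT201 exposure, and the baseline is over-subtracted after withdrawal.

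The net direction cannot be determined from the documents. Cmax is the main worry for upward contamination of low-dose exposure. AUClast is affected modestly by a short ERT overlap, but by more if low-dose participants stay on ERT: 0.89, 0.80 or 0.61 at c = 0.5, 1 or 3 if Cohort 1 is on ERT for all 38 weeks and the other cohorts for 5 (y = 38r + 38c in Cohort 1).

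Every slope here rests on assumed ERT sizes, flat and exactly proportional FLT201 activity, and, outside step 7, all participants being ERT users. The figures show sensitivity and do not forecast the result.

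**What to change.** In SAP 10.3 and 10.4:

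1. Flag each GCase sample as on or off ERT, using the dates on the Gaucher Treatment eCRF page.
2. Report Cmax, AUC over a common window and the power-model slope twice. One version uses all samples. The other uses off-ERT samples only, after a washout fixed by the study pharmacokineticist before lock and before any resumption.
3. Run the off-ERT version with and without subtraction of the on-ERT baseline. Filtering samples alone does not restore a slope of 1, as the right-hand column in step 5 shows.
4. State how many participants in each cohort contribute to each version.
5. Base any statement about dose proportionality on whether the versions agree.

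Separately, Protocol 8.1 and 11.3.1 must be reconciled on when ERT/SRT is withdrawn, because the flag and the expected length of overlap depend on it.

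**Cost.** SAP text and extra programming, with no new data collection. The off-ERT version omits participants never taken off ERT. That selects on GCase response, probably most at low doses, so it should not stand alone or replace the all-sample version. An off-ERT AUC window also differs from the baseline-to-Week-38 AUC named in the protocol, and should be labelled as such.
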